**NOTES:**

- If the study treatment stop date is missing then the AE will be considered to be On-Treatment.

### 10.4.4. Treatment Phases for Concomitant Medication

Study Phase	Definition
Prior	If medication end date is not missing and is before 28 days prior to screening visit
Concomitant	Any medication that is not a prior

**NOTES:**

- Please refer to [Appendix 7](#): Reporting Standards for Missing Data for handling of missing and partial dates for concomitant medication. Use the rules in this table if concomitant medication date is completely missing.

## 10.5. Appendix 5: Data Display Standards & Handling Conventions

### 10.5.1. Reporting Process

Software	

 
The currently supported versions of SAS software and WIN-NonLin will be used.
 
	
Reporting Area	
HARP Server	: UK1SALX00175
HARP Area	Final : \arprod\gsk2982772\mid205017\final_01
QC Spreadsheet	: \arwork\gsk2982772\mid205017\documents
Analysis Datasets	

 
Analysis datasets will be created according to Legacy GSK A&R dataset standards.
 
	
Generation of RTF Files	

 
RTF files will be generated for SAC tables.
 
	

### 10.5.2. Reporting Standards

General	

 
The current GSK Integrated Data Standards Library (IDSL) will be applied for reporting, unless otherwise stated (IDSL Standards Location: https://spope.gsk.com/sites/IDSLLibrary/SitePages/Home.aspx):           
 
4.03 to 4.23: General Principles
 
5.01 to 5.08: Principles Related to Data Listings
 
6.01 to 6.11: Principles Related to Summary Tables
 
7.01 to 7.13: Principles Related to Graphics
 
 
 
Do not include subject level listings in the main body of the GSK Clinical Study Report. All subject level listings should be located in the modular appendices as ICH or non-ICH listings
 
All data displays (Tables, Figures & Listings) will use the term "Subject" which reflects CDISC and GSK Data Display Standards terminology.
 
	
Formats	
	
 
All data will be reported according to the actual treatment the subject receives unless otherwise stated.
 
GSK IDSL Statistical Principles (5.03 & 6.06.3) for decimal places (DP's) will be adopted for reporting of data based on the raw data collected, unless otherwise stated.
 
Numeric data will be reported at the precision collected on the eCRF.
 
The reported precision from non eCRF sources will follow the IDSL statistical principles but may be adjusted to a clinically interpretable number of DP's.
 
PK Summary Statistics: 3 significant figures for the lowest value of each PK parameter. The summary statistics for higher values will be reported to the same number of decimal places as the lowest value
 

Planned and Actual Time	
	
 
Reporting for tables, figures and formal statistical analyses:           
 
Planned time relative to dosing will be used in figures, summaries, statistical analyses and calculation of any derived parameters, unless otherwise stated.
 
The impact of any major deviation from the planned assessment times and/or scheduled visit days on the analyses and interpretation of the results will be assessed as appropriate.
 
 
 



• Reporting for Data Listings:

• Planned and actual time relative to study drug dosing will be shown in listings (Refer to IDSL Statistical Principle 5.05.1).

• Unscheduled or unplanned readings will be presented within the subject's listings.

	
Unscheduled Visits	

• Unscheduled visits will not be included in summary tables and/or figures.

• All unscheduled visits will be included in listings.

	
Descriptive Summary Statistics	
Continuous Data	Refer to IDSL Statistical Principle 6.06.1
Categorical Data	N, n, frequency, %
Reporting of Pharmacokinetic Concentration Data	
Descriptive Summary Statistics	Refer to IDSL Statistical Principle 6.06.1 Assign zero to NQ values (Refer to GUI_51487 for further details)
Graphical Displays	

• Refer to IDSL Statistical Principals 7.01 to 7.13.

	

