9.4.3. Electrocardiograms

- Triplicate 12-lead ECGs will be obtained at screening and single 12-lead ECGs will be obtained as outlined in the SoA using an ECG machine that automatically calculates the heart rate and measures PR, QRS, QT, and QTc intervals. If a single ECG shows a QTc increase of ≥ 60 msec from baseline (pre-dose Day 1), two further ECGs should be performed over a brief period (e.g. 5 to 10 minutes) and the assessment made on the mean QTc of the triplicate ECGs. Refer to Section 8.1.2 for QTc withdrawal criteria and additional QTc readings that may be necessary.
- The QTc should be based on averaged QTc values of triplicate ECGs obtained over a brief (e.g. 5 to 10 minutes) recording period.
- The acceptable deviations from the nominal ECG measurement time points are:
 - The pre-dose ECG measurements will be taken ≤ 2 hours before dosing
 - Post-dose ECG measurements will be taken ± 15 minutes from the nominal post-dose time point.
 - Discharge ECG measurements will be taken ± 1 hour from the nominal time point.
- ECGs are to be measured after participant has been in a semi-supine or supine position after approximately 5 minutes rest.
- If a participant shows an abnormal assessment at any stage, repeat measurements may be made and the abnormality followed to resolution if required. Additional measurements may be taken as deemed necessary by the investigator.
- Any clinically significant abnormality, including changes from baseline (pre-dose Day 1), will be reported as an AE.

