12.6. Appendix 6: Liver Safety: Required Actions and Follow-up Assessments

Phase I liver chemistry stopping criteria and required follow up assessments

Liver Chemistry Stopping Criteria	
ALT-absolute	
ALT\geq3xULN
 
If ALT\geq3xULN AND bilirubin^{1,2} \geq 2xULN (>35% direct bilirubin) or INR >1.5, Report as an SAE.
 
See additional Actions and Follow Up Assessments listed below

Required Actions and Follow up Assessments	
Actions	Follow Up Assessments

 • Immediately discontinue study treatment • Report the event to GSK within 24 hours • Complete the liver event CRF, and complete an SAE data collection tool if the event also meets the criteria for an SAE² • Perform liver event follow up assessments • Monitor the subject until liver chemistries resolve, stabilise, or return to within baseline (see MONITORING below) 
MONITORING:
 
If ALT\geq3xULN AND bilirubin \geq 2xULN or INR >1.5
 
 • Repeat liver chemistries (include ALT, AST, alkaline phosphatase, bilirubin) and perform liver event follow up assessments within 24 hrs • Monitor participants twice weekly until liver chemistries resolve, stabilise or return to within baseline • A specialist or hepatology consultation is recommended 
If ALT\geq3xULN AND bilirubin < 2xULN and INR \leq1.5:
 
 • Repeat liver chemistries (include ALT, AST, alkaline phosphatase, bilirubin) and perform 	
 • Viral hepatitis serology³ • Obtain INR and recheck with each liver chemistry assessment until the transaminases values show downward trend • Obtain blood sample for pharmacokinetic (PK) analysis, obtained within 2 days of last dose⁴ • Serum creatine phosphokinase (CPK) and lactate dehydrogenase (LDH). • Fractionate bilirubin, if total bilirubin\geq2xULN • Obtain complete blood count with differential to assess eosinophilia • Record the appearance or worsening of clinical symptoms of liver injury, or hypersensitivity, on the AE report form • Record use of concomitant medications on the concomitant medications report form including paracetamol/acetaminophen, herbal remedies, other over the counter medications. • Record alcohol use on the liver event alcohol intake case report form 
If ALT\geq3xULN AND bilirubin \geq 2xULN or INR >1.5:

Liver Chemistry Stopping Criteria	

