## 5.2. Baseline Definitions

For all endpoints (except as noted in baseline definitions) the baseline value will be the latest pre-dose assessment with a non-missing value, including those from unscheduled visits. If time is not collected, Day 1 assessments are assumed to be taken prior to first dose and used as baseline.

Parameter	Study Assessments Considered as Baseline			Baseline Used in Data Display
	Screening	Day -1	Day 1 (Pre-Dose)	
Safety				
Vital signs	X	X	X	Day 1 (Pre-Dose)
12-lead ECG	X	X	X	Day 1 (Pre-Dose)
Laboratory (Haematology, clinical chemistry and urinalysis)	X	X	X	Day 1 (Pre-Dose)

Unless otherwise stated, if baseline data is missing no derivation will be performed and baseline will be set to missing.

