2.15.	Safety	LIVER1	Summary of Liver Monitoring/Stopping Event Reporting: Part A	IDSL	SAC
2.16.	Safety	LIVER10	Summary of Hepatobiliary Laboratory Abnormalities: Part A		SAC
ECG					
2.17.	Safety	EG1	Summary of ECG Findings: Part A	IDSL	SAC
2.18.	Safety	EG2	Summary of Change from Baseline in ECG Values by Visit: Part A	IDSL	SAC
2.19.	Safety	CP_EG12	Summary of Maximum Change from Baseline in QTc Values by Category: Part A	IDSL	SAC

Safety : Tables					
No.	Population	IDSL / TST ID / Example Shell	Title	Programming Notes	Deliverable [Priority]
Vital Signs					
2.20.	Safety	VS1	Summary of Change From Baseline in Vital Signs by Visit: Part A	ICH E3 Includes Baseline values.	SAC
2.21.	Safety	VS1	Summary of Vital Signs by Visit: Part A		SAC

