## 10.11.6. Safety Figures

### 10.11.6.1. Safety Figures Part A

Safety : Figures					
No.	Population	IDSL / TST ID / Example Shell	Title	Programming Notes	Deliverable [Priority]
Adverse Events					
2.1.	Safety	AE10	Plot of Common Adverse Events and Relative Risk: Part A	IDSL	SAC
Hepatobiliary (Liver)					
2.2.	Safety	LIVER14	Scatter Plot of Maximum vs Baseline for ALT: Part A		SAC
2.3.	Safety	LIVER9	Scatter Plot for Maximum ALT vs Maximum Total Bilirubin: Part A		SAC

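### The SAP keeps unscheduled visits out of summary tables and figures with no exception for maximum or worst-case displays, so protocol-required liver and laboratory repeats cannot count towards the maximum shown

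*SAP*

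**What the plan says.** The exclusion rule is in SAP 10.5.2 (Reporting Standards): "Unscheduled visits will not be included in summary tables and/or figures". The same section adds "All unscheduled visits will be included in listings" and, under data listings, "Unscheduled or unplanned readings will be presented within the subject's listings". SAP 10.3.1 defines no analysis windows and bases summaries on nominal visits. SAP 5.2 treats baseline differently: "the baseline value will be the latest pre-dose assessment with a non-missing value, including those from unscheduled visits".

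The SAP plans several displays whose content is an extreme value. For Part A these are Figure 2.2 (maximum against baseline ALT), Figure 2.3 ("Scatter Plot for Maximum ALT vs Maximum Total Bilirubin: Part A"), Table 2.10 (emergent chemistry results by PCI criteria), Table 2.16 (hepatobiliary abnormalities), Table 2.66 (worst-case lipids) and Table 2.19 ("Summary of Maximum Change from Baseline in QTc Values by Category: Part A"). Parts B and C have counterparts.

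The protocol calls for extra measurements in three situations:
- **Liver.** After ALT of at least 3xULN, Appendix 6 requires repeat chemistries within 24 hours, or within 24 to 72 hours in the milder branch. Monitoring then follows, weekly in the milder branch and otherwise "Monitor participants twice weekly until liver chemistries resolve, stabilise or return to within baseline".
- **Other laboratory tests.** Section 9.4.4 asks for repeats of values judged clinically significantly abnormal.
- **QTc.** After a single-ECG increase of 60 msec or more, section 9.4.3 says "two further ECGs should be performed over a brief period (e.g. 5 to 10 minutes) and the assessment made on the mean QTc", meaning the average over all three readings.

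**The concern.** A maximum or worst-case display exists to show the most extreme value a participant reached. The values most likely to be extreme are those taken while an abnormality is being followed, and these fall outside the Schedule of Activities. A rule suited to by-visit means, where unscheduled values would distort the denominators, has been applied to displays with the opposite purpose.

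Safety and tolerability is a secondary objective and is summarised descriptively, so these tables and figures are the safety evidence in the body of the report. If the peak is found on a repeat, a figure titled as a maximum shows something lower. The plot of maximum ALT against maximum bilirubin is the most exposed, because its use is to reveal participants who are high on both.

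**Working it through.** The documents give no figure to reproduce. The check sets the rules side by side and applies them to one assumed case.

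**1. Is there a route for an off-schedule value into a summary?** SAP 10.5.2 excludes unscheduled visits without qualification. SAP 10.3.1 provides no window that could assign such a value to a planned visit. SAP 10.6.1 has a rule for choosing between two values in a window, but it points to 10.3.1, which defines none. SAP 10.7.1 carries only planned data from withdrawn participants into tables and figures. The SAP applies the sponsor's reporting standards unless otherwise stated; their content is not in the documents, so no exception can be assumed from them. No written route exists.

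**2. What is scheduled?** Protocol Table 1 (Parts A and C) has laboratory panels on Day -1 of every period, pre-dose in Period 1 only, 24 hours post-dose in every period, and at follow-up. With all six periods run, the scheduled panels after the first dose number 6 (24 h) + 5 (Day -1 of Periods 2 to 6) + 1 (follow-up) = 12. A participant with ALT of at least 3xULN stops treatment (Appendix 6) and leaves the study after follow-up assessments (Protocol 8.2). From then on the only scheduled panel is the follow-up/discontinuation visit, 7 days after the last dose. The repeat and the weekly or twice-weekly monitoring are not in the Schedule of Activities.

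**3. Assumed case.** Scheduled 24 h sample: ALT 3.2xULN, bilirubin 1.2xULN. Appendix 6 repeat: ALT 8xULN, bilirubin 2.2xULN, direct fraction above 35%. Later values are lower.

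| Criterion | Scheduled values only | All values |
|---|---|---|
| Point plotted in Figure 2.3 (ALT, bilirubin) | 3.2, 1.2 | 8, 2.2 |
| Protocol combined SAE criterion (ALT ≥3xULN and bilirubin ≥2xULN) | not met (1.2 < 2) | met (8 ≥ 3; 2.2 ≥ 2) |
| SAP Appendix 8 ALT flag (≥2xULN) | met | met |
| SAP Appendix 8 bilirubin flag (≥1.5xULN) | not met (1.2 < 1.5) | met (2.2 ≥ 1.5) |
| SAP Appendix 8 combined flag (bilirubin 1.5xULN with ALT ≥2xULN) | not met | met |

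The participant still appears with raised ALT. What is lost is the height of the peak and the joint elevation.

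**4. Lipids.** The worst-case lipid table classifies values as outside the normal range or not. A repeat ordered because a scheduled lipid was abnormal comes from someone already out of range, so a more extreme repeat in the same direction should not change that status. The rule reaches this table, but the practical effect is the smallest.

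**5. Baseline.** Under 5.2 an unscheduled pre-dose value can be the baseline. Under 10.5.2 an unscheduled post-dose value cannot be the maximum compared with it. SAP 10.6.1 also refers to a row covering any post-baseline visit, which sits awkwardly with the exclusion.

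**6. QTc.** Confirmatory ECGs come within about 5 to 10 minutes of a scheduled ECG, whose own tolerance is ±15 minutes. Suppose (assumed) the single reading is +65 msec and the triplicate mean +50 msec. If 10.5.2 drops the confirmatory readings, the table shows +65, in the category of 60 or more. If the rule in 10.6.1 for multiple measurements at one time point applies, it shows +50, in the category between 30 and 60. The SAP does not say which.

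**7. Size of one case.** Parts A and C enrol 16 and may dose up to 24; Part B enrols 10 and may dose up to 15. One participant is 1/24 = 4.2%, 1/16 = 6.25%, 1/15 = 6.7% or 1/10 = 10%.

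**The case against.** The strongest reply is that little is lost. A scheduled abnormal value that triggers a repeat stays in the display. All unscheduled data are listed, and Listings 19 and 20 cover values of potential clinical importance. Table 2.15 summarises liver monitoring and stopping events, and clinically relevant laboratory changes are recorded as adverse events. All this stands and limits the harm. It does not correct the figures: the SAP keeps subject-level listings out of the report body, nothing indicates that Table 2.15 shows peak values, and a listing could contain a value that the matching table implies did not occur.

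A reader might also infer more than the documents support:
- **That unscheduled values are barred from everything.** They are not; 5.2 admits them as baseline.
- **That the QTc table drops the confirmatory ECGs.** The SAP excludes unscheduled visits, and these readings are taken minutes after a scheduled one, so 10.6.1 may average them.
- **That any abnormal value triggers a mandatory repeat.** Appendix 6 starts at ALT of 3xULN, and 9.4.4 depends on clinical significance. A repeat after, say, 2.9xULN is required only if the investigator judges that value clinically significant. Repeat ECGs outside the QTc rule are optional.
- **That there is only one scheduled safety panel per period.** The Day -1 panels in Periods 2 to 6 also follow earlier doses.

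**Conclusion.** The point holds for the liver and laboratory displays. Followed as written, SAP 10.5.2 and 10.3.1 leave protocol-required off-schedule chemistries out of the maximum-ALT and ALT-versus-bilirubin plots and of the hepatobiliary, emergent-PCI and worst-case lipid tables. The displayed maximum is understated only in a participant whose off-schedule value exceeds every scheduled one. The documents give no basis for estimating how often that will happen, and the ALT and bilirubin values used above are illustrative. In a plot, the effect is a single point in the wrong place.

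For QTc the finding is an ambiguity between 10.5.2 and 10.6.1, not a demonstrated error. The point concerns reporting only. It does not touch the pharmacokinetic objectives or the individual stopping rules, which do not depend on these tables. It should be settled before the final safety tables are programmed.

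**What to change.** Amend SAP 10.5.2 to say that unscheduled values stay out of by-visit summaries, while all post-baseline values, scheduled and unscheduled, enter every maximum, worst-case, emergent-PCI and hepatobiliary table and figure in Parts A, B and C. Add that where confirmatory ECGs were taken under Protocol 9.4.3, the maximum-QTc table uses the triplicate mean, with a cross-reference to SAP 10.6.1. This matches the value on which the protocol bases its own assessment.

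The cost is a sentence or two and a programming flag. No new data are collected. The safety displays may look slightly less favourable.

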## 10.6. Appendix 6: Derived and Transformed Data

### 10.6.1. General

Multiple Measurements at One Analysis Time Point

 
If there are two values within a time window (as per Section 10.3.1) the value closest to the target day for that window will be used. If values are the same distance from the target, then the mean will be taken.
 
Mean of the measurements will be calculated and used in any derivation of summary statistics but if listed, all data will be presented.
 
Participants having both High and Low values for Normal Ranges at any post-baseline visit for safety parameters will be counted in both the High and Low categories of "Any visit post-baseline" row of related summary tables. This will also be applicable to relevant Potential Clinical Importance summary tables.
 

Study Day

 
Calculated as the number of days from First Dose Date: 
 
Ref Date = Missing → Study Day = Missing
 
Ref Date < First Dose Date → Study Day = Ref Date – First Dose Date
 
Ref Date ≥ First Dose Date → Study Day = Ref Date – (First Dose Date) + 1
 
 
 

### 10.6.2. Study Population

Demographics
Age

 
GSK standard IDSL algorithms will be used for calculating age where birth date will be imputed as follows: 
 
Any subject with a missing day will have this imputed as day '15'.
 
Any subject with a missing date and month will have this imputed as '30th June'.
 
 
 
Birth date will be presented in listings as 'YYYY'.
 

Body Mass Index (BMI)

 
Calculated as Weight (kg) / [Height (m)]
 

Extent of Exposure

 
Number of days of exposure to study drug will be calculated based on the formula:  Duration of Exposure in Days = Treatment Stop Date – (Treatment Start Date) + 1 
 
Participants who were randomized but did not report a treatment start date will be categorised as having zero days of exposure.
 
The cumulative dose will be based on the formula:  Cumulative Dose = Sum of (Number of Days x Total Daily Dose) 
 
If there are any treatment breaks during the study, exposure data will be adjusted accordingly.
 

### 10.6.3. Safety

ECG Parameter
RR Interval

 
IF RR interval (msec) is not provided directly, then RR can be derived as :           
 
[1] If QTcB is machine read & QTcF is not provided, then :
 
 <math display="block">RR = \left[ \left( \frac{QT}{QTcB} \right)^2 \right] * 1000</math> 
 
[2] If QTcF is machine read and QTcB is not provided, then:
 
 <math display="block">RR = \left[ \left( \frac{QT}{QTcF} \right)^3 \right] * 1000</math> 
 
If ECGs are manually read, the RR value preceding the measurement QT interval should be a collected value THEN do not derive.
 

Corrected QT Intervals

 
When not entered directly in the eCRF, corrected QT intervals by Bazett's (QTcB) and Fridericia's (QTcF) formulas will be calculated, in msec, depending on the availability of other measurements.
 
IF RR interval (msec) is provided then missing QTcB and/or QTcF will be derived as
 
 $QTcB = \frac{QT}{\sqrt[4]{\frac{RR}{1000}}}$ $QTcF = \frac{QT}{\sqrt[3]{\frac{RR}{1000}}}$

Laboratory Parameters

 
If a laboratory value which is expected to have a numeric value for summary purposes, has a non-detectable level reported in the database, where the numeric value is missing, but typically a character value starting with '<x' or '>x' (or indicated as less than x or greater than x in the comment field) is present, the number of decimal places in the observed values will be used to determine how much to add or subtract in order to impute the corresponding numeric value.           
 
Example 1: 2 Decimal Places= '< x ' becomes x - 0.01
 
Example 2: 1 Decimal Places = '> x' becomes x + 0.1
 
Example 3: 0 Decimal Places = '< x' becomes x - 1
 
 
 

### 10.6.4. Pharmacokinetic

#### 10.6.4.1. Non-Compartmental Analysis

The pharmacokinetic parameters will be calculated by standard non-compartmental analysis according to current working practices using WinNonlin Version 6.3 or higher.

Pharmacokinetic Endpoints
AUC(0-t)

 
Area under the concentration-time curve from time zero to the time of the last quantifiable concentration (C(t)) will be calculated using the linear trapezoidal rule for each incremental trapezoid and the log trapezoidal rule for each decremental trapezoid.
 

Pharmacokinetic Endpoints	
AUC(0-∞) (Day 1)	

 
Area under the concentration-time curve extrapolated to infinity will be calculated as:  <math display="block">AUC = AUC(0-t) + C(t) / \lambda_z</math> 
where <math>\lambda_z</math> is the terminal phase rate constant.
 
 
	
AUC(0-24) for QD dosing	
Area under the concentration-time curve from time zero to 24 h post dose will be calculated using the linear trapezoidal rule for each incremental trapezoid and the log trapezoidal rule for each decremental trapezoid.	
AUC(0-12) for BID dosing	
Area under the concentration-time curve from time zero to 12 h post dose will be calculated using the linear trapezoidal rule for each incremental trapezoid and the log trapezoidal rule for each decremental trapezoid.	
AUC(12-24) for BID dosing	
Area under the concentration-time curve from time 12 h to 24 h post dose will be calculated using the linear trapezoidal rule for each incremental trapezoid and the log trapezoidal rule for each decremental trapezoid.	
AUC%extrap	
Percentage of AUC extrapolated beyond the last measured time point	
Cmax	
Maximum observed concentration, determined directly from the concentration-time data	
C12h for BID dosing	
Observed concentration at 12 hours, determined directly from the concentration-time data	
C24h	
Observed concentration at 24 hours, determined directly from the concentration-time data	
Tmax	
Time to reach C max , determined directly from the concentration-time data.	
Tlag	
Time from dosing at which GSK2982772 was first quantifiable in a concentration vs time profile	
t1/2	
Terminal half-life	
Notes	

 
Additional parameters may be included as required
 
	

Relative Bioavailability (F rel )	

 
Frel will be calculated as follows:
 
	
$F_{rel} = \frac{GeoMean\{AUC \text{ or } C_{max}(\text{test})\}}{GeoMean\{AUC \text{ or } C_{max}(\text{reference})\}} \times 100$	
F rel will be calculated using AUC (0-∞) and C max . If for any reason the AUC (0-∞) is not calculable then an alternative AUC such as AUC (0-last) , AUC (0-T) or AUC over a partial area may be used. The following comparisons will be made: 
 
MR Formulation (test) vs IR Formulation (reference)
 
Fed (test) vs Fasted (reference)
 
Day 3 vs Day 1 (reference)
 
	

